- Proportion who require at least one COVID-19 related medically attended visit for management/treatment of COVID-19 (apart from routinely scheduled study-directed visits) which may occur in any setting through Day 29 (e.g., Emergency department, urgent care, outpatient clinic or professional setting wherein direct in-person/telemedicine medical assessment and escalation of care for COVID-19 is provided by licensed healthcare personnel).
- Proportion of subjects who require hospital admission for medical care (non-quarantine purposes) through Day 29.
- If admitted to hospital post randomization: Duration of hospital stay through Day 29.
- Proportion of subjects who require ICU admission or initiation of ICU-level care\* through Day 29.
- If admitted to ICU post randomization: Duration of ICU stay through Day 29.
- Proportion of subjects requiring invasive mechanical ventilation through Day 29.
- If requiring invasive mechanical ventilation post randomization: Duration of invasive mechanical ventilation through Day 29.
- All-cause mortality through Day 29.
- Incidence of critical COVID-19 illness, defined as any one of the following: (a) requiring ICU admission or ICU level of care\*, (b) invasive mechanical ventilation, or (c) resulting in death by Day 29.
- Length of time to clinical progression to critical COVID-19 illness through Day 29 (defined as the time to death, invasive mechanical ventilation, or ICU admission/requiring ICU level of care).

[\*Note: ICU level care is defined as the medical need for intensive or invasive monitoring; immediate or impending need for the support of the airway, breathing, or circulation; and/or stabilization of acute severe or life-threatening complications of COVID-19]

After this interim analysis, the 1 gram dose arm may be terminated, the trial may be terminated (if the 2 gram dose is discontinued, the 1 gram dose will also be terminated), or the study will continue as originally planned unless discontinued for business or feasibility reasons in a setting of changing epidemic dynamics in the geographic catchment of the trial.

The futility analysis will not inflate the type I error since the trial will not be stopped to claim efficacy. The primary outcome will be analyzed according to Section 9.1.

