# 3.2 Treatment

### 3.2.1 Randomization Scheme and Treatment Arm Assignment

Eligible subjects will be randomized 1:1:1 to Placebo or to C19-IG 20% via a SC infusion on Day 1 at a dose of either 1 gram or 2 grams, according to the randomized dose assigned. A central randomization stratified by age group (age <65 years versus  $\geq$  65 years) will be used for this study. Randomization will be centralized and will be performed via an Interactive Web Response System after subject inclusion. A randomization list containing the randomization numbers and the corresponding randomized treatment assignments will be generated and stored in a secured area that is only accessible to the randomization team.

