### 4.2 Analysis Populations

The following four analysis populations will be defined for this study:

The intent-to-treat (ITT) population is defined as all subjects who are randomized.

The modified intent-to-treat (mITT) population is defined as the subset of subjects included in the ITT who are also dosed. The mITT population will be used for all efficacy analyses. As sensitivity analysis, the primary efficacy analysis will also be carried out using the ITT population if different from the mITT population.

The Per-Protocol (PP) population is defined as the subset of subjects included in the mITT population who do not present major protocol violations which might have an impact on the primary efficacy endpoint(s), and complete at least 80% of the IP. The primary efficacy analyses will be carried out using the PP population if different from the mITT population.

The Safety (SAF) population is defined as subjects who receive at least any amount of blinded C19-IG 20%/Placebo. All safety analyses will be carried out using the SAF population based on the treatment actually received rather than randomized treatment.

The validity of a subject for inclusion in each of these populations (ITT, mITT, Safety, and PP) will be assessed before unblinding the database and documented in a blinded review report.

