#### 6.1 Primary Efficacy Endpoint and Analysis

The primary efficacy analysis will be carried out on the mITT population. The analysis will be repeated using the ITT and PP population if different from the mITT population,

The primary efficacy variable is the proportion of asymptomatic subjects who remain asymptomatic through Day 14. Subject clinical features/symptoms and radiographical evidence of pneumonia will be recorded in the database; the oxygen saturation by pulse oximetry on room air will be recorded daily through Day 14 by subject at home on the "SpO2 and Temperature Log", as well as on the "Patient's Measured Oxygen Saturation" eCRF at the protocol-specified healthcare provider visits. In the case when multiple SpO2 values are recorded on the same day, the lower value will be used for the analysis.

The null hypothesis is that the proportion of subjects who meet the primary endpoint in a given C19-IG 20% dose group (2 g and 1 g) will be no different than the proportion of subjects in placebo group; H0:  $\pi_t - \pi_c = 0$ . The alternative hypothesis is that the proportion of subjects who meet the primary endpoint at Day 14 in a given C19-IG 20% dose group will be different than the proportion

of subjects in placebo;  $H_1$ :  $\pi_t - \pi_c \neq 0$ .

Separate comparisons will be made for each C19-IG 20% dose group. If the 2 g dose group fails to demonstrate superiority compared to placebo at two-sided significance level of 5%, the test for 1 g dose group compared with placebo will be considered as exploratory rather than as confirmatory.

The proportion of subjects who meet the primary endpoint within each treatment group will be presented along with a two-sided exact (Clopper-Pearson) 95% confidence interval (CI).

The observed difference in the proportion of subjects who meet the primary endpoint between each C19-IG 20% dose group and placebo along with the exact unconditional 95% CI for risk difference will be calculated. The null hypothesis will be tested using Chi-square statistic and the p-value will be reported.

Sensitivity analysis on primary endpoint will be performed using the Cochran-Mantel-Haenszel (CMH) test, stratified by randomization strata (age <65 years versus  $\geq$  65 years). The common risk difference in the proportion of subjects meeting the primary endpoint between each C19-IG 20% dose group and placebo, together with the associated 95% CIs and p-value will be presented.

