- If admitted to ICU post randomization: Duration of ICU stay through Day 29.
- Proportion of subjects requiring invasive mechanical ventilation through Day 29.
- If requiring invasive mechanical ventilation post randomization: Duration of invasive mechanical ventilation through Day 29.
- All-cause mortality through Day 29.
- Incidence of critical COVID-19 illness, defined as any one of the following: (a) requiring ICU admission or ICU level of care\*, (b) invasive mechanical ventilation, or (c) resulting in death by Day 29.
- Length of time to clinical progression to critical COVID-19 illness through Day 29 (defined as the time to death, invasive mechanical ventilation, or ICU admission/requiring ICU level of care).

After this interim analysis, the 1 gram dose arm may be terminated, the trial may be terminated (if the 2 gram dose is discontinued, the 1 gram dose will also be terminated), or the study will continue as originally planned unless discontinued for business or feasibility reasons in a setting of changing epidemic dynamics in the geographic catchment of the trial.

The futility analysis will not inflate the type I error since the trial will not be stopped to claim efficacy. The primary and key secondary efficacy outcomes will be analyzed using the methods described above in Section 6.1 and 6.2. No subgroup or sensitivity analyses are planned for the futility analysis.

Suppose at the time of data-cut for the futility analysis,  $x_0$  subjects meet the primary efficacy endpoint among  $m_0$  subjects in the placebo group, and  $x_1$  subjects have events among  $m_1$  subjects in the treatment group (1 gram or 2 grams C19-IG 20%). Let  $\tilde{p}_g = x_g/m_g$  for group g = 0, 1; and  $\tilde{p} = (x_0 + x_1)/(m_0 + m_1)$ .  $Z_1 = \frac{\tilde{p}_1 - \tilde{p}_0}{\sqrt{(m^{-1} + m^{-1})\tilde{p}(1 - \tilde{p})}}$  is the z-score corresponding to the Chi-

square statistic.

Let the final sample size be  $n_0$  and  $n_1$  in the placebo and treated (1 gram or 2 grams C19-IG 20%)

0

1

groups respectively. Let  $Z_{1-\alpha/2}$  be the 1-  $\alpha/2 = 97.5\%$  percentile of the normal distribution, which

can be calculated as the PROBIT function in SAS. Let  $t = (n_0^{-1} + n_1^{-1})/(m_0^{-1} + m_1^{-1})$ . The conditional power (CP) for the primary efficacy endpoint (each of C19-IG 20% dose groups compares to placebo) will be calculated using the formula:

$$CP = 1 - \Phi \left( \frac{Z_{1-\alpha/2} - Z_1/\sqrt{t}}{\sqrt{1-t}} \right)$$

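### If the 1 g arm closes alone at the interim, no rule limits its comparison to placebo subjects randomized while 1 g was open

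*SAP*

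**What the plan says.** **Closing one arm.** SAP 9 and Protocol 9.3 provide that "After this interim analysis, the 1 gram dose arm may be terminated, the trial may be terminated". If 2 g is discontinued, 1 g stops too, so 1 g can close alone only when 2 g and placebo go on.

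**Who is analysed.** SAP 4.2: "The mITT population will be used for all efficacy analyses". That population "is defined as the subset of subjects included in the ITT who are also dosed". It is not limited by enrolment date.

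**How.** SAP 6.1: "Separate comparisons will be made for each C19-IG 20% dose group", and "The null hypothesis will be tested using Chi-square statistic and the p-value will be reported". Protocol 9.1 allows Fisher's exact or chi-square. The only stratified analysis is a CMH sensitivity analysis using the randomization strata, which are age only (SAP 3.2.1: "A central randomization stratified by age group"). The other repeats of the primary analysis use the ITT and PP sets and, if needed, treatment received. SAP 6.2 applies the same each-dose-against-placebo pattern to the secondary endpoints.

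**After the interim.** Protocol 9.3 ends: "The primary outcome will be analyzed according to Section 9.1". The hierarchy in SAP 4.5 still lists 1 g against placebo as its second hypothesis. Under SAP 6.1 that test becomes exploratory if 2 g fails.

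No section says how a closed 1 g arm is analysed.

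**The concern.** Once 1 g closes, new subjects can be assigned only to 2 g or placebo. Those later placebo subjects are not randomized controls for 1 g. They differ from the 1 g subjects in calendar time, and in a pandemic calendar time can change variant, prior immunity and testing practice, and so the proportion who stay free of symptoms. If they are pooled, the 1 g estimate is the dose effect plus a share of that drift. A fall in late placebo success makes 1 g look beneficial, and a rise makes it look harmful. Neither the unadjusted chi-square nor the age-stratified CMH test removes this.

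At stake is the 1 g result only: confirmatory if 2 g wins, exploratory but still reported if it does not. If the analysis set stays open, it would also have to be chosen once the later placebo data exist.

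**Working it through.** **Inputs from the documents.** 267 per arm, allocated 1:1:1; 80% of placebo assumed to remain asymptomatic; design effect 10 points; two-sided 5% tests; the z-score and conditional power (CP) formulas in SAP 9.

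**Inputs assumed, because the documents give none.** Number per arm when 1 g closes (m): 80, 133 or 200. The futility look is set by calendar date. 133 per arm is the size of the DSMB safety review and serves here only as a middle value. Late placebo success p: 70% to 90%. Stopping rule: CP below 20% for 1 g and at least 20% for 2 g. Placebo reaches 267, and 2 g to placebo stays 1:1.

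**Step 1. The plan's own figure.** With the unpooled two-proportion formula, two-sided alpha 0.025 and 80% power:

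n = (0.80×0.20 + 0.90×0.10) × (2.241 + 0.842)² / 0.10² = 0.25 × 9.505 / 0.01 ≈ 238 per arm, as stated. Rounded to 240, 240/0.90 ≈ 267.

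The planning rate and arm size used below are therefore the plan's own.

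**Step 2. Bias when 1 g has no effect.** 1 g subjects are all early, with success 0.80. Pooled placebo has expected success (m×0.80 + (267−m)×p)/267, so

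bias = (267−m)/267 × (0.80 − p).

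| Close at m per arm | Late share of placebo | p = 70% / 90% | p = 75% / 85% |
|---|---|---|---|
| 80 | 187/267 = 0.700 | +7.0 / −7.0 points | +3.5 / −3.5 |
| 133 | 134/267 = 0.502 | +5.0 / −5.0 | +2.5 / −2.5 |
| 200 | 67/267 = 0.251 | +2.5 / −2.5 | +1.3 / −1.3 |

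At p = 80% the bias is zero.

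**Step 3. False findings, given that 1 g alone stops.** Averaging over all trials would count those in which 1 g looked good and stayed open. The simulation therefore draws early data for the three arms, applies the SAP 9 conditional power formula, keeps only trials in which 1 g stops and 2 g continues, adds late placebo subjects, and tests 1 g against placebo at two-sided 5%. 1 g has no effect; 2 g truly adds 10 points.

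| Close at m per arm | Falsely worse, p = 90% | Falsely better, p = 70% |
|---|---|---|
| 80 | about 45% | about 10% |
| 133 | about 28% | about 9% |
| 200 | about 10% | about 3% |
| Concurrent placebo only, any m | about 2% | 0% |

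At 133 per arm:
- A 5-point shift gives about 10% falsely worse (p = 85%) or 1.4% falsely better (p = 75%).
- If 2 g is also ineffective, 1 g closes alone in roughly 10% of trials. Among those, a 10-point shift gives about 19% falsely worse or 8% falsely better.

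**Step 4. Cost of restricting placebo.** At 133 per arm and 80% success, the 95% half-width for the 1 g difference is 1.96 × √(0.16 × (1/133 + 1/133)) ≈ 9.6 points. With all 267 placebo subjects it is 1.96 × √(0.16 × (1/133 + 1/267)) ≈ 8.3 points.

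**The case against.** **Nothing states the pooling.** A reader might infer that the plan prescribes comparing 1 g with the whole placebo arm. It does not say so. Pooling follows from the mITT definition, the separate comparisons and the lack of any concurrency rule. The Protocol 9.3 sentence sending the primary outcome to Section 9.1 sits in the interim section, and its SAP counterpart can be read as governing the interim analysis itself. This stands: the defect is an unspecified analysis set whose literal reading is biased.

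**The documents do not forecast drift in the endpoint.** A reader might take "in a setting of changing epidemic dynamics in the geographic catchment of the trial" as such a forecast. The phrase qualifies discontinuation for business or feasibility reasons. It makes drift plausible but does not quantify it.

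**Unconditional rates overstate the risk.** At 133 per arm, a test over all simulated trials rejects in about 19% (p = 70%) or 25% (p = 90%). A futility stop selects poor early 1 g results, so false benefit is lower than that: at 133 per arm a 5-point fall gives 1.4%, below the nominal 2.5% in one direction. The conditional figures in Step 3 are the relevant ones.

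**The 1 g test is gated.** It is confirmatory only after 2 g wins. If neither dose works, rejecting both hypotheses at p = 70% occurs in about 0.2% of all trials. This limits the confirmatory risk mainly to large drift with an effective 2 g dose. The reported 1 g estimate remains biased either way.

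**Two further readings go too far.** Distortion of a dose-response or pooled-dose result is not at issue, because none is planned. Nor can 2 g against placebo be called unaffected without qualification: that needs the 2 g to placebo allocation to stay constant, and the ratio after closure is not stated.

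**Conclusion.** The concern holds as a gap in specification. If 1 g closes alone, neither document limits its comparison to concurrently randomized placebo subjects, and the literal reading admits drift into the 1 g estimate. With a 10-point late shift the bias is about 7.0, 5.0 or 2.5 points for closure at 80, 133 or 200 per arm; a 5-point shift gives half that, and no drift gives none. For comparison, the trial is sized on a 10-point effect. The larger testing risk is a false finding against 1 g when late placebo success rises; a false benefit is less frequent.

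These sizes rest on assumed closure size, drift and CP threshold, and on CP alone deciding the stop, whereas the plan also weighs secondary outcomes. The point is worth settling because the remedy is short, but it concerns a contingent comparison of the second dose and does not threaten the primary 2 g test if allocation stays 1:1.

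**What to change.** Add to SAP 6.1, 6.2 and 9, before the interim is unblinded:

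- If the 1 g arm is closed early, every 1 g versus placebo comparison uses only placebo subjects randomized on or before the last 1 g randomization date.
- Any analysis of 1 g against all placebo subjects is a sensitivity analysis adjusted for enrolment period.
- 2 g versus placebo uses all subjects, provided 2 g to placebo allocation stays 1:1 after closure. If it changes, that comparison is stratified by period.

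This takes a few SAP sentences and a date filter. The price is precision in the 1 g comparison only: a half-width of about 9.6 instead of 8.3 points if closure is at 133 per arm, where power for 80% against 90% at two-sided 5% is about 63%. The filter removes the drift bias. It does not remove the usual downward selection from stopping for futility: with a 1 g CP below 20% and no true effect, the concurrent estimate averages about −1.5 points at 133 per arm. The report should say so.

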#### 4.6 Data Derivations and Transformations

The following derivations will be used in this study:

Study Day:

- Date of assessment date of study drug administration + 1 for assessments done on or after date of study drug administration
- Date of assessment date of study drug administration for assessments done before date of study drug administration

Baseline Observation: the last non-missing value prior to study drug administration.

Duration:

• Duration in days = end date - start date + 1

• Duration in minutes = end time in minutes – start time in minutes

Origin or Start Date for Time to Event Endpoints:

- Time to negative SARS-CoV-2 by PCR: date of study drug administration
- Time to Clinical Progression: date of study drug administration
- Time to COVID-19 symptoms through Day 14: date of study drug administration

Event Date for Time to negative SARS-CoV-2 by PCR:

• The date of the first negative result from the SARS-CoV-2 assessment by PCR will be used as the event date for deriving time to negative SARS-CoV-2.

Event Date for Time to Clinical Progression

• The event date will be the date of death, the start date of invasive mechanical ventilation, or the date of ICU admission/requiring ICU level of care, whichever occurs first.

Event Date for Time to COVID-19 symptoms through Day 14

• The event date will be the first time point when any element of the case definition for primary efficacy variable is fulfilled through Day 14

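### SAP 9 does not define the same outcome in both arms for the conditional-power counts: placebo subjects who meet the primary endpoint, but treated subjects who have events

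*SAP*

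**What the plan says.** SAP 9 describes the data at the interim cut as x0 placebo subjects who "subjects meet the primary efficacy endpoint among" m0, and x1 treated subjects who "subjects have events among" m1. Both counts go into one definition of the arm proportion, x_g/m_g for g = 0 and 1, and into one pooled proportion. Z1 is the treated-minus-placebo difference over its pooled standard error and "is the z-score corresponding to the Chi"-square statistic. On the final quantity SAP 9 says: "conditional power (CP) for the primary efficacy endpoint (each of C19-IG 20% dose groups compares to placebo) will be calculated using the formula". Written out, that is CP = 1 − Φ((z − Z1/√t)/√(1 − t)), where z is the 97.5th normal percentile.

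Other sections use the two phrases as follows:

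- SAP 6.1: "The primary efficacy variable is the proportion of asymptomatic subjects who remain asymptomatic through Day 14". It continues: "The proportion of subjects who meet the primary endpoint within each treatment group will be presented". Meeting the endpoint is therefore the favourable outcome.
- SAP 4.6, in its derivation for the secondary time-to-symptoms endpoint: "The event date will be the first time point when any element of the case definition for primary efficacy variable is fulfilled". For this case definition, the event is the unfavourable outcome.

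SAP 9 does not define an event, does not equate the two phrases, and does not say which sign of Z1 favours C19-IG 20%. Protocol 9.3 describes the futility analysis without a formula. Neither document gives a conditional-power cut-off.

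**The concern.** Z1 is signed and conditional power is an upper tail, so a high value arises only when the treated proportion exceeds the placebo proportion. That is the right orientation if the proportions are of subjects who stay well. If they are of subjects who become ill, the sign of Z1 reverses. If one is of each, Z1 compares unlike quantities.

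A programmer can follow the sentence literally, or can harmonise it in either direction. Two of those three implementations give an effective dose a conditional power near zero. Conditional power is the only numerical criterion named for the interim decision. That decision may end the 1 g arm or the whole trial, and 1 g stops if 2 g is discontinued. The quantity should not depend on a guess about what is counted.

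**Working it through.** **Inputs.** SAP 10 assumes 80% of placebo and 90% of treated subjects remain asymptomatic, with about 240 per arm before a 10% allowance for withdrawals and 267 after it. The documents print no conditional-power value to reproduce. The design figure does reproduce: with two-sided alpha 0.025 and 80% power, (2.241 + 0.842)² × (0.80 × 0.20 + 0.90 × 0.10)/0.10² = 237.6, which rounds up to the stated 238.

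**Assumption.** The look is timed by calendar (December 2021), so its size is not stated. I take m = 120 and n = 240 per arm for illustration, then vary both.

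**Formula.** With equal arms, t = (2/n)/(2/m) = m/n = 0.5. The SAP expression is the conditional power under the current trend. Starting from 1 − Φ((z − Z1√t − (Z1/√t)(1 − t))/√(1 − t)), the two Z1 terms sum to Z1/√t, which gives the SAP form. The algebra and the information fraction are correct.

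**Observed pattern 80% versus 90% asymptomatic, m = 120, n = 240**

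(A) Remaining asymptomatic counted in both arms, 96 and 108:
- pooled p = 204/240 = 0.85
- SE = √((2/120) × 0.85 × 0.15) = 0.0461
- Z1 = 0.10/0.0461 = +2.17 and Z1/√t = 3.07
- CP = 1 − Φ((1.96 − 3.07)/0.707) = 1 − Φ(−1.57) = 0.94

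(B) Becoming symptomatic counted in both arms, 24 and 12:
- same SE, Z1 = −2.17
- CP = 1 − Φ((1.96 + 3.07)/0.707) = 1 − Φ(7.11) ≈ 6 × 10⁻¹³

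(C) Literal text with SAP 4.6's meaning of event, 96 placebo successes and 12 treated events:
- pooled p = 108/240 = 0.45
- SE = √((2/120) × 0.45 × 0.55) = 0.0642
- Z1 = −0.70/0.0642 = −10.9
- CP effectively 0

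**A harmful dose, 80% versus 70% asymptomatic, same m and n.** Under (A), Z1 = −1.79 and CP ≈ 1 × 10⁻¹⁰. Under (B), Z1 = +1.79 and CP = 0.79. Under (C), CP is again effectively 0, as it is for a dose with no effect, so (C) does not discriminate at all.

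**Range for 80% versus 90%, counts rounded to whole subjects**

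| m per arm | Asymptomatic, placebo / treated | Z1 under (A) | CP (A), n = 240 | CP (A), n = 267 |
|---|---|---|---|---|
| 67 | 54 / 60 | +1.45 | 0.82 | 0.86 |
| 133 | 106 / 120 | +2.40 | 0.97 | 0.979 |
| 200 | 160 / 180 | +2.80 | 0.997 | 0.995 |

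In all six cells, CP under (B) is at most about 1.4 × 10⁻⁸ and under (C) it is effectively 0.

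**The case against.** The strongest reply is that SAP 9 largely answers the question itself. It sends the primary outcome to the methods of 6.1, where the difference is treated minus placebo in the proportion meeting the endpoint, and Z1 keeps that orientation. One definition of the arm proportion serves both arms, and a pooled proportion makes sense only if both arms count the same thing. The result is labelled as conditional power for the primary endpoint. Nor is the word event always adverse: SAP 4.6 also gives an event date for a first negative PCR, which is favourable. This stands. It makes reading (A) the probable intention, and on that reading nothing in the formula is wrong.

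A reader might infer that the upper-tail form is a defect. It is not: a one-directional conditional power is normal for futility in a superiority trial. It matters here only because the counted outcome is unsettled.

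A reader might also infer that a miscoded value would stop the trial. The documents do not support that. No cut-off is stated, secondary outcomes also inform the decision, and an independent unblinded team reviews the output. Under 6.1 that output includes each arm's proportion asymptomatic, so 90% against 80% would sit beside a conditional power near zero. Reading (C) would be especially conspicuous.

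What remains is that no sentence fixes the count or the sign. The symptom event of SAP 4.6 is also at work inside SAP 9, because time to COVID-19 symptoms heads its list of secondary outcomes. Double programming (SAP 4.1) would expose two different readings, but not one misreading shared by both programmers. Reading (B) is the harder one to spot, because its Z1 of −2.17 looks plausible.

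**Conclusion.** The point holds as an inconsistent definition in a decision formula. It does not show that the wrong quantity will be computed. On the probable reading, the planned effect gives conditional power of about 0.94 at an assumed 120 of 240 per arm. On the literal reading, or with symptom events in both arms, it gives a value near 0. The contrast does not depend on the assumed interim size: it persists for 67 to 200 per arm and for a final 240 or 267. The figures assume that the observed proportions equal the planning values. The consequence is a futility review that could be given a misleading number, with the other output available to contradict it.

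**What to change.** In SAP 9, define x_g for g = 0 and 1 as the number of subjects, among the m_g assessed, who remain asymptomatic through Day 14 (that is, who do not fulfil the case definition). Drop the reference to events in the treated arm, and state that Z1 > 0 favours C19-IG 20%.

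A worked programming check is optional: 96 of 120 placebo and 108 of 120 treated subjects asymptomatic, with a final 240 per arm, should return Z1 = 2.17 and CP = 0.94. Label those m and n as illustrative, since the SAP fixes neither the interim size nor n0 and n1 in the formula.

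The cost is a sentence or two, to be in place before the December 2021 look. The change alters no design feature and has no effect on type I error.
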